2 INTRODUCTION

This statistical plan addresses the planned analyses for the WallFlex Biliary FC Chronic Pancreatitis RCT based on the protocol dated 17 January 2012, Version AB. All of the specified analyses may not be provided in reports to Competent Authorities but may be used for scientific presentations and/or manuscripts. The primary analysis will be based on the data through 24 months post-procedure.

Version AA March 20, 2013 Boston Scientific WallFlex Biliary FC CP RCT SAP 90913894/Ver. AA Page 7 of 13

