4.2. Secondary Endpoints

1. Occurrence of adverse events related to the stent and/or the stent placement or removal procedures
2. Number of ERCP procedures through 24 months after initial stent placement
3. Ability to deploy the stent(s) in satisfactory position
4. Stent Removal:
 - Ability to remove the stent(s) without serious stent removal related adverse events at each procedure involving removal of stent(s) (technical success at removal) or
 - Complete distal migration without serious stent removal related adverse events
5. Liver Function Tests (LFT's)
 - Baseline LFTs compared to LFTs taken at time of original plastic stent placement for any subject with a prior plastic stent
 - LFT improvement at 1 month post-study treatment compared to baseline LFTs (and/or compared to LFTs taken at time of original plastic stent placement for any subject with a prior plastic stent)
 - LFTs at month 24 compared to LFTs at removal of last stent (applicable for subjects who had not been re-stented at time of month 24 visit)
6. Health Economic Endpoints:
 - Number of outpatient procedures
 - Number of hospitalizations
 - Duration of hospitalizations

- Length of procedures
- Number of devices

5. Design

The study is designed as a post-market, multi-center, prospective, non-blinded, randomized study. At least 164 subjects (82 per arm) will be treated with 1:1 randomization between Group A and Group B and will be followed through 24 months post-initial stent(s) placement:

- Subjects in the MS arm will be treated with a single metal stent, which will be removed 12 months post-placement.
- Subjects in the PS arm will receive 2 plastic stents when possible. Subjects in this arm will undergo plastic stents exchange/bile duct calibration at 4 and 8 month post-initial stent placement. At each stent exchange, the goal should be to provide progressive stent therapy by increasing the number of plastic stents at 4 months and again at 8 months. Final plastic stent removal will occur 12 months post-initial stent placement.

5.1. Inclusion Criteria:

- Age 18 or older
- Willing and able to comply with the study procedures and provide written informed consent to participate in the study
- Chronic pancreatitis

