8.1. Objective

Rate of Stricture Resolution in the Metal Stent group is non-inferior to the Plastic Stent group.

Statistical testing will be performed to determine if the rate of stricture resolution for the metal stent is non-inferior to the plastic stent group. The null hypothesis is that the rate of stricture resolution is non-inferior in the Metal Stent Arm versus the Plastic Stent Arm:

$H_0: \pi_{test} - \pi_{control} \geq \Delta$ (Inferior)

$H_a: \pi_{test} - \pi_{control} < \Delta$ (Non-inferior)

February 15, 2013

FINAL

where π_{test} and $\pi_{control}$ are the probabilities of having a stricture resolution in the metal stent arm and the plastic stent arm respectively, and Δ is defined as the non-inferiority margin.

The sample size was calculated for a one-sided 0.050 Farrington-Manning test using SAS 9.2®. If the P value from the Farrington-Manning test is <0.05 then the metal stent group will be considered non-inferior to the plastic stent group. The expected probability of a stricture resolution in the metal stent arm and plastic stent arm is 66.0%, which was taken from the 95% CIs from the meta-analysis below. The non-inferiority margin (Δ) is 20%. Given these assumptions, and a one-sided 5% significance level, $2 \times 74 = 148$ subjects will provide 80% power to reject the null hypothesis, that the metal stent group is inferior to the plastic stent group. To compensate for possible loss of subjects between randomization and complete assessment of inclusion/exclusion criteria, an additional 10% of subjects will be enrolled for a total of $2 \times 82 = 164$.

8.2. *Justification for Study Design and Sample Size Calculations*

- A literature search of metal and or plastic stenting for treatment of benign biliary strictures secondary to chronic pancreatitis yielded 4 articles representing 70 subjects treated with metal stenting (MS)²⁻⁷ and 3 articles representing 60 subjects treated with plastic stenting (PS)⁸⁻¹³.
- The following meta-analysis was conducted of the probability of stricture resolution:
 - Metal Stenting: A meta-analysis of the stricture resolution rate during the reported follow-up after initial stent placement yields a proportion of 0.762 [95% CI: 0.593 – 0.895]²⁻⁷.
 - Plastic Stenting: A meta-analysis of the stricture resolution rate during the reported follow-up after initial stent placement yields a proportion of 0.611 [95% CI: 0.311 – 0.870]⁸⁻¹³.

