Version AA March 20, 2013 Boston Scientific WallFlex Biliary FC CP RCT SAP 90913894/Ver. AA Page 3 of 13

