1 PROTOCOL SUMMARY

Full Title	A Multi-Center, Prospective, Randomized Study Comparing Removable, Self-Expanding Metal Stents to Plastic Stents for the Treatment of Benign Biliary Strictures Secondary to Chronic Pancreatitis		
Short Title	WallFlex Biliary FC Chronic Pancreatitis RCT		
Primary Objective	To compare the use of Self Expanding Metal Stents (SEMS) to plastic stents for the treatment of benign biliary strictures secondary to chronic pancreatitis as it pertains to stricture resolution rates, complication rates and number of ERCP procedures during 24 months.		
Study Devices	Group A: Metal Stents – MS Arm WallFlex [™] Biliary RX Fully Covered Stent System RMV		
	Group B. Plastic Stents – PS Arm Per Investigator preference		
Study Design	Prospective, multi-center, randomized		
Planned Number of Subjects	164		
Planned Number of Sites	Up to 15		
Primary Endpoint	Stricture resolution at 24 months		
Secondary Endpoints	 Occurrence of adverse events related to the stent and/or the stent placement or removal procedures 		
	 Number of ERCP procedures through 24 months after initial stent placement 		
	3. Ability to deploy the stent(s) in satisfactory position		
	4. Stent Removal:		
	• Ability to remove the stent(s) without serious stent removal related adverse events at each procedure involving removal of stent(s) (technical success at removal) or		
	• Complete distal migration without serious stent removal related adverse events		
	5. Liver Function Tests (LFT's):		

Version AA March 20, 2013 Boston Scientific WallFlex Biliary FC CP RCT SAP 90913894/Ver. AA Page 4 of 13

	continue until Month 24 after initial stent placement for all subjects, in order to assess all secondary endpoints in a comparative fashion for the MS and PS arms.	
Key Inclusion	• Age 18 or older	
Criteria	• Willing and able to comply with the study procedures and provide written informed consent to participate in the study	
	Chronic pancreatitis	
	• Stricture not previously dilated or stricture previously dilated with no more than one plastic stent of 10 Fr or less for 6 months or fewer	
	• Symptomatic bile duct stricture (defined by cholangitis or persistent jaundice for at least one month or cholestasis associated with at least 3 times normal alkaline phosphatase levels) documented at time of enrollment for naïve stricture or at the time of one prior plastic stent placement up to 6 months before enrollment in strictures that had one prior plastic stent inserted. ¹²	

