4 GENERAL STATISTICAL METHODS

4.1 Analysis Sets

Primary endpoint and selected secondary endpoints will be done for the following cohorts.

Enrolled Cohort

A subject is considered "enrolled" after signing the study-specific ICF. Subjects who sign the ICF but subsequently do not meet one or more of the selection criteria will be considered screen failures and excluded from the study.

Intent-to-Treat Cohort (ITT)

This cohort consists of those "enrolled" subjects who meet all inclusion/exclusion criteria and are subsequently randomized. Subjects in this cohort who do not receive a study stent(s) will be counted towards the enrollment ceiling. Any adverse events occurring or resulting from a treatment attempt will be collected. Protocol deviations will be collected as necessary.

Per-Protocol Cohort (PP)

The per-protocol cohort is a subset of the ITT subjects who receive the study stent(s) as randomized and no major protocol deviations (Per ICH E9).

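### The SAP cites a January 2012 protocol and departs from the February 2013 one on secondary items, per-protocol wording and one eligibility phrase; separately, both documents make ITT conditional on eligibility

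*SAP*

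**What the plan says.** - **Version.** The SAP's page header reads "Version AA March 20, 2013". Its section 2 says the plan is "based on the protocol dated 17 January 2012, Version AB". The protocol's page footer, visible in section 8.1, reads "February 15, 2013" and is marked final.
- **Secondary items.** Protocol 4.2 opens its liver-test list with "Baseline LFTs compared to LFTs taken at time of original plastic stent placement for any subject with a prior plastic stent" and closes its health-economic list with "Number of devices". Neither is in SAP 5.1.
- **Month-1 liver tests.** Protocol 4.2 compares month 1 with baseline, and/or with the values at the original plastic stent. SAP 5.1 item 5a uses baseline for naïve strictures, or the values at the prior stent if that stent was placed within 6 months of enrolment.
- **Per-protocol cohort.** SAP 4.1 requires the stent received to be the one assigned. Protocol 8.4.3 requires only that a study stent was received. Both also exclude major deviations.
- **Eligibility text.** The SAP synopsis has a criterion beginning "Stricture not previously dilated or stricture previously dilated with no more than one plastic stent", followed by limits on size and duration. It wants symptoms in previously stented subjects documented "at the time of one prior plastic stent placement up to 6 months before enrollment". Protocol 5.1 and 5.2 limit the number, calibre and duration of prior stenting, but not when the stent was placed.
- **ITT.** SAP 4.1 defines ITT as enrolled "subjects who meet all inclusion/exclusion criteria and are subsequently randomized". Protocol 8.4.2 has the same definition. Protocol 8.1 justifies the extra 10% of subjects by loss after randomisation and before eligibility assessment is complete.

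**The concern.** A SAP should be written against the protocol it serves. This one names a version more than a year older than the protocol in force when it was dated, and its content does not fully match that protocol. An analyst who follows SAP 5.1 would leave two protocol secondary items without a planned analysis, would apply a different month-1 liver-test comparison, and would build the per-protocol set from different words.

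The ITT definition is a second matter. If membership depends on meeting the criteria and eligibility can be settled after randomisation, subjects can leave the ITT set once their assignment is known. The trial is not blinded, so this is the kind of exclusion that an ITT set exists to prevent.

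**Working it through.** The plan states no figure on this point, so the check is mainly a comparison of text.

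**1. Dates.** From 15 February to 20 March 2013 is 13 + 20 = 33 days. The February 2013 protocol therefore carried its date about a month before the SAP did.

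**2. Secondary items.**

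| | Protocol 4.2 | SAP 5.1 | Missing from SAP 5.1 |
|---|---|---|---|
| Liver-test comparisons | 3 | 2 | baseline against original plastic stent |
| Health-economic items | 5 | 4 | device count |

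The SAP liver items are lettered a and b in sequence, and the health-economic list runs straight into the next paragraph, so the gap is not a lost page. The endpoint list in the SAP synopsis is incomplete in the available text, so the omission is shown for SAP 5.1 only. A footnote to Protocol Table 1 requires the original-stent liver tests in addition to baseline, so those data should exist.

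**3. Month-1 comparator.** Under the protocol, a previously stented subject can be compared with baseline, with the original-stent values, or with both. Under SAP 5a the same subject is compared with the original-stent values only, and has no stated comparator if that stent was placed more than 6 months before enrolment. Protocol 7.4.1 also words the baseline liver tests as an either/or, which does not sit well with its own Table 1 footnote.

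**4. Who is classified differently?** The prior-dilation criterion, read in full, allows no prior dilation or one plastic stent of limited size and duration. For prior stenting this largely restates the exclusion that both documents carry. Only the placement-date phrase can separate them. For a single prior stent of permitted size:

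| Placed before enrolment | Time in place | Protocol 5.1/5.2 | SAP synopsis |
|---|---|---|---|
| 6 months or less | 6 months or less | in | in |
| more than 6 months | more than 6 months | out | out |
| more than 6 months | 6 months or less | in | out |

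Only the third row diverges; a stent placed 9 months earlier and removed after 3 is an example.

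**5. ITT.** The conditional definition is the same in SAP 4.1 and Protocol 8.4.2. The documents place eligibility and randomisation in different orders. Protocol 7.4.2 allows randomisation only after all criteria are verified, and SAP 3.1.2 puts the expected loss before randomisation. Protocol 8.1 puts it after.

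**6. Size.** The inputs are the expected rate of 66% and 74 per arm (SAP 3.1.2). 0.66 × 74 = 48.84, taken as 49 resolved; 49/74 = 66.2%.

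- Drop one responder: 48/73 = 65.8%, a change of -0.46 points.
- Drop one failure: 49/73 = 67.1%, a change of +0.91 points.

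The number affected is not given. As an outer limit, assume an arm of 82 loses the whole allowance of 82 - 74 = 8, all with the same outcome. 0.66 × 82 = 54.12, taken as 54; 54/82 = 65.9%.

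- All eight responders: 46/74 = 62.2%, a change of -3.7 points.
- All eight failures: 54/74 = 73.0%, a change of +7.1 points.

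This is an arithmetic bound, not a forecast. Losses unrelated to outcome would leave the rate unchanged on average.

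**The case against.** The best defence is that little of this reaches the results. The divergent eligibility phrase sits in a synopsis of key criteria to which SAP 4.1 does not refer. Randomisation follows verification under Protocol 7.4.2, so a condition on eligibility should rarely bite. Per-protocol exclusion turns on major protocol deviations, and a subject eligible under the protocol has no eligibility deviation. Both missing items are pre-specified in Protocol 4.2, and Protocol 8.6.2 undertakes to report secondary endpoints by group with differences and 95% intervals. The missing liver-test item compares two values taken before study treatment, so it cannot inform the treatment effect. SAP 5.6 already provides for documented changes.

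Most of that stands as to size. It does not repair SAP 5.1, which is the SAP's operative endpoint list, or Protocol 8.1, which expects loss after randomisation.

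A reader might infer more than the documents support:

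- *That the old protocol version caused the omissions.* The January 2012 protocol is not available, and a mistyped citation is possible. The recurrence of the 6-month enrolment limit in both the synopsis and item 5a fits a superseded source, but does not prove one.
- *That the prior-dilation criterion removes subjects.* Its second half permits the single prior stent.
- *That the ITT wording comes from the version mismatch.* The February 2013 protocol has it too, so updating the SAP would reproduce it.
- *That the two items would be lost.* Protocol 4.2 and 8.6.2 still commit to them.
- *That each dropped subject moves a rate by 1/74, or 1.35 points.* That is the effect of reversing one outcome, not of removing one subject at a rate near 66%.

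**Conclusion.** The point holds as two findings. First, the SAP cites a protocol other than the one in hand and differs from it in two omitted secondary items, the month-1 liver-test comparator, the per-protocol wording and one eligibility phrase with a narrow reach. Second, and independent of version, both documents condition ITT on eligibility while Protocol 8.1 leaves room for removal after randomisation.

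The likely numerical effect on the primary comparison is small: about -0.5 or +0.9 points in one arm per subject dropped, assuming 74 per arm and resolution near 66%. The number of such subjects is unknown. SAP 4.1 runs the primary endpoint on the enrolled, ITT and per-protocol cohorts without naming one as primary, so it cannot be said that the primary analysis set is the one affected. The primary endpoint definition, hypotheses as printed, test, margin, alpha and sample size match. The changes are worth making before analysis because they are cheap and go beyond clerical correction.

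**What to change.** In one SAP revision, approved before analysis as SAP 5.6 provides:

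1. Cite the governing protocol version in section 2.
2. Add the device count and the baseline-against-original-stent liver-test comparison to section 5.1.
3. Align the month-1 liver-test comparator with Protocol 4.2, and settle the Protocol 7.4.1 wording against the Table 1 footnote.
4. Use one per-protocol definition in both documents.
5. Have the sponsor reconcile the eligibility passages, or have the SAP refer to Protocol 5.1 and 5.2 instead of restating them. Which text governs is for the sponsor to decide.
6. Define ITT as all randomised subjects, analysed by assigned arm regardless of later eligibility findings, and make the same change in Protocol 8.4.2. Changing only the SAP would create a new conflict.

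The cost is one SAP revision and a short protocol change, with whatever approvals Protocol section 12 requires. The restored liver-test comparison needs no new data if the Table 1 footnote is followed.

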3 ENDPOINT ANALYSIS

3.1 Primary Endpoint

The rate of stricture resolution is the primary endpoint for the study.

3.1.1 Hypotheses

Statistical testing will be performed to determine if the rate of stricture resolution for the metal stent is non-inferior to the plastic stent group. The null hypothesis is that the rate of stricture resolution is non-inferior in the Metal Stent Arm versus the Plastic Stent Arm:

Ho: $\pi_{test} - \pi_{control} \ge \Delta$ (Inferior)

Ha: $\pi_{test} - \pi_{control} < \Delta$ (Non-inferior)

where π_{test} and $\pi_{control}$ are the probabilities of having a stricture resolution in the metal stent arm and the plastic stent arm respectively, and Δ is defined as the non-inferiority margin.

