Key Exclusion Criteria	
 • Biliary stricture of benign etiology other than chronic pancreatitis • Prior biliary metal stent or any plastic stenting other than one plastic stent of 10 Fr or less for 6 months or fewer • Developing obstructive biliary symptoms associated with an attack of acute pancreatitis • Biliary stricture of malignant etiology • Stricture within 2 cm of common bile duct bifurcation • Known bile duct fistula or leak • Subjects for whom endoscopic techniques are contraindicated • Known sensitivity to any components of the stent or delivery system • Symptomatic duodenal stenosis (with gastric stasis) • Participation in another investigational study within 90 days prior to consent • Investigator Discretion
Statistical Hypothesis	
A literature search of metal and plastic stenting for treatment of benign biliary strictures secondary to chronic pancreatitis yielded 4 articles representing 70 subjects treated with metal stenting (MS)^{1,9-11} and 3 articles representing 60 subjects treated with plastic stenting (PS)^{3,4,8}.
 
The following meta-analysis was conducted of the probability of stricture resolution:
 
 • Metal Stenting: A meta-analysis of the stricture resolution rate during the reported follow-up after initial stent placement yields a proportion

of 0.762 [95% CI: 0.593 – 0.895]^{1,9-11}.

- **Plastic Stenting:** A meta-analysis of the stricture resolution rate during the reported follow-up after initial stent placement yields a proportion of 0.611 [95% CI: 0.311 – 0.870]^{3,4,8}.

Statistical testing will be performed to determine if the rate of stricture resolution for the metal stent is non-inferior to the plastic stent group. The null hypothesis is that the stricture resolution rate is non-inferior in the Metal Stent Arm versus the Plastic Stent Arm:

$$H_0: \pi_{test} - \pi_{control} \geq \Delta \text{ (Inferior)}$$

$$H_a: \pi_{test} - \pi_{control} < \Delta \text{ (Non-inferior)}$$

where π_{test} and $\pi_{control}$ are the probabilities of having a stricture resolution in the metal stent arm and the plastic stent arm respectively, and Δ is defined as the non-inferiority margin.

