8.6.2. Post-Procedure Endpoints

Post-procedure information will be collected at regularly scheduled follow-up examinations as detailed in the clinical trial schedule and will be summarized using descriptive statistics for continuous variables and frequency statistics for discrete variables. Estimates of primary and secondary endpoints will be reported by treatment group, as well as differences between treatment groups and their 95% confidence intervals.

Impact of baseline variables on endpoints will be analyzed using logistic regression, ANOVA, stratified methods or Kaplan-Meier methods per section 8.6.1 and the SAP.

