	• Common bile duct stricture based on imaging assessment of dilatation of the common and/or intrahepatic bile ducts	
Key Exclusion	• Biliary stricture of benign etiology other than chronic pancreatitis	
	• Any prior biliary metal stent or any plastic stenting other than one plastic stent of 10 Fr or less for 6 months or fewer	
	• Developing obstructive biliary symptoms associated with an attack of acute pancreatitis	
	Biliary stricture of malignant etiology	
	• Stricture within 2 cm of common bile duct bifurcation	
	Known bile duct fistula or leak	
	• Subjects for whom endoscopic techniques are contraindicated	
	• Known sensitivity to any components of the stent or delivery system	
	• Symptomatic duodenal stenosis (with gastric stasis)	
	• Participation in another investigational study within 90 days prior to consent	
	Investigator Discretion	
Statistical Hypothesis	A literature search of metal and plastic stenting for treatment of benign biliary strictures secondary to chronic pancreatitis yielded 4 articles representing 70 subjects treated with metal stenting (MS) ^{1,9-11} and 3 articles	

Version AA March 20, 2013 Boston Scientific WallFlex Biliary FC CP RCT SAP 90913894/Ver. AA Page 6 of 13

representing 60 subjects treated with plastic stenting (PS) ^{3,4,8} .
The following meta-analysis was conducted of the probability of stricture resolution:
 Metal Stenting: A meta-analysis of the stricture resolution rate during the reported follow-up after initial stent placement yields a proportion of 0.762 [95% CI: 0.593 – 0.895]^{1,9-11}. Plastic Stenting: A meta-analysis of the stricture resolution rate during the reported follow-up after initial stent placement yields a proportion of 0.611 [95% CI: 0.311 – 0.870]^{3,4,8}.
Statistical testing will be performed to determine if the rate of stricture resolution for the metal stent is non-inferior to the plastic stent group. The null hypothesis is that the stricture resolution rate is non-inferior in the Metal Stent Arm versus the Plastic Stent Arm:
Ho: $\pi_{test} - \pi_{control} \ge \Delta$ (Inferior)
Ha: $\pi_{test} - \pi_{control} < \Delta$ (Non-inferior) where π_{test} and $\pi_{control}$ are the probabilities of having a stricture resolution in the metal stent arm and the plastic stent arm respectively, and Δ is defined as the non-inferiority margin.

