3.1.2 Sample Size

A literature search of metal and or plastic stenting for treatment of benign biliary strictures secondary to chronic pancreatitis yielded 4 articles representing 70 subjects treated with metal stenting (MS)²⁻⁷ and 3 articles representing 60 subjects treated with plastic stenting (PS)⁸⁻¹³.

The following meta-analysis was conducted of the probability of stricture resolution:

- Metal Stenting: A meta-analysis of the stricture resolution rate during the reported follow-up after initial stent placement yields a proportion of 0.762 [95% CI: 0.593 0.895]²⁻⁷.
- Plastic Stenting: A meta-analysis of the stricture resolution rate during the reported follow-up after initial stent placement yields a proportion of 0.611 [95% CI: 0.311 0.870] ⁸⁻¹³.

The sample size was calculated for a one-sided 0.050 Farrington-Manning test using SAS 9.2®. If the P value from the Farrington-Manning test is <0.05 then the metal stent group will be considered non-inferior to the plastic stent group. The expected probability of a stricture resolution in the metal stent arm and plastic stent arm is 66.0%, which was taken from the 95% CIs from the meta-analysis above. The non-inferiority margin (Δ) is 20%. Given these assumptions, and a one-sided 5% significance level, 2 x 74 = 148 subjects will provide 80% power to reject the null hypothesis, that the metal stent group is inferior to the plastic stent group. To compensate for possible loss of subjects between enrollment and complete assessment of inclusion/exclusion criteria and subsequent randomization, an additional 10% of subjects will be enrolled for a total of 2 x 82 = 164.

Version AA March 20, 2013 Boston Scientific WallFlex Biliary FC CP RCT SAP 90913894/Ver. AA Page 8 of 13

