7.3 Rules and Definitions

Binary event rates (proportions) will be reported on a per patient basis.

The last follow-up date will be the latest of the following dates for each patient: date of an adverse event, index procedure date, follow-up visit date, any stent or ECRP procedure date, stent removal date, and device event date.

Stricture resolution at 24 months is defined by the following two criteria being met:

• Absence of re-stenting after the per-protocol stenting period through the 24 month visit

Version AA March 20, 2013 Boston Scientific WallFlex Biliary FC CP RCT SAP 90913894/Ver. AA Page 12 of 13 • Absence of cholestasis at the 24 month visit, defined as alkaline phosphatase level not exceeding 2 times the level at completion of the per-protocol stenting period

Primary endpoint failures are 1) subjects who are re-stented during follow-up after the per-protocol stenting period and 2) subjects who have not been re-stented at month 24 but have alkaline phosphatase level exceeding 2 times the level at completion of the per-protocol stenting period.

Subjects who experience early stent removal or complete distal stent migration without subsequent re-stenting will not be considered failures. If re-stenting occurs, but the cumulative stenting period does not exceed 12 months, the subject remains eligible for primary endpoint assessment.

For the final tables, two-sided exact tests will be done to test for differences between the two groups for removability and AEs. A one-sided non-inferiority Farrington-Manning test will be done to see if stricture resolution is non-inferior in the Metal group compared to the Plastic group. A two-sided student's t-test will done to test for differences between the two groups for the number of ERCP procedures done.

Version AA March 20, 2013 Boston Scientific WallFlex Biliary FC CP RCT SAP 90913894/Ver. AA Page 13 of 13

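### The primary non-inferiority hypotheses are written in the wrong direction in all four places, and no passage states the correct null value or tail

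*SAP*

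**What the plan says.** SAP 3.1.1 defines the two π terms, which "are the probabilities of having a stricture resolution in the metal stent arm and the plastic stent arm respectively", and takes the difference as test minus control. Its lead sentence reads "The null hypothesis is that the rate of stricture resolution is non-inferior in the Metal Stent Arm versus the Plastic Stent Arm". The alternative is displayed as "Ha: $\pi_{test} - \pi_{control} < \Delta$ (Non-inferior"), and the null is the complement, labelled inferior.

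The block occurs four times: protocol synopsis (Statistical Hypothesis), protocol 8.1, SAP section 1 and SAP 3.1.1. The protocol synopsis has "The null hypothesis is that the stricture resolution rate is non-inferior in the Metal Stent Arm versus the Plastic Stent Arm", and SAP section 1 displays "Ho: $\pi_{test} - \pi_{control} \ge \Delta$ (Inferior").

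The sample-size text, in the protocol synopsis, protocol 8.1, SAP section 1 and SAP 3.1.2, sets Δ at 20% without a sign. It specifies a one-sided 5% Farrington-Manning test with p < 0.05 as the criterion, and 80% power "to reject the null hypothesis, that the metal stent group is inferior to the plastic stent group". SAP 7.3, which specifies the final test, says only: "A one-sided non-inferiority Farrington-Manning test will be done to see if stricture resolution is non-inferior".

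**The concern.** For a good outcome, non-inferiority means that metal is not worse than plastic by the margin or more, so the null must sit at metal − plastic = −20 points and be rejected for large differences. The displayed inequalities say something else. With Δ = +20 points, a metal stent that is 20 points better falls under *inferior*, and one that is 40 points worse falls under *non-inferior*. Each lead sentence also makes non-inferiority the null, which contradicts the label on the H0 line below it and the sample-size text.

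This is the only test in the plan with a stated p-value criterion for a claim. The p < 0.05 rule does not settle direction, because the p-value depends on the null value and the tail. If the displayed hypotheses were coded, the primary conclusion could be reversed. If they are not coded, the analyst departs from the formal hypotheses in an unblinded trial and has to justify that choice by inference.

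**Working it through.** **Inputs.** 66.0% resolution in both arms, Δ = 20%, one-sided α = 0.05, 80% power, 74 per arm evaluable and 82 per arm enrolled (SAP 3.1.2). Meta-analysis rates of 76.2% (metal) and 61.1% (plastic) (SAP 3.1.2).

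**1. The plan's own figure.** Under the intended null (difference −0.20), the restricted maximum-likelihood estimates at 66% v 66% are 0.5466 and 0.7466.

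- s0 = √(0.5466×0.4534 + 0.7466×0.2534) = 0.661
- s1 = √(2×0.66×0.34) = 0.670
- n = [(1.645×0.661 + 0.842×0.670)/0.20]² ≈ 68.2, so 69 per arm (70 with unpooled variance)

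The stated 74 is not reproduced exactly. It is slightly conservative: power at 74 is 82.8% by this approximation and 83.2% by exact enumeration. A null of +0.20 with a lower-tailed test also gives n = 68.2, because the equal-rates case is symmetric. The sample size therefore cannot show which direction was used.

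**2. Either sign of Δ.** Three rules, each using z = (p_M − p_P − δ0)/SE, with SE from the restricted estimates and critical value 1.645:

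- Literal, Δ = +0.20: δ0 = +0.20, reject if z < −1.645.
- Literal, Δ = −0.20: δ0 = −0.20, reject if z < −1.645.
- Intended: δ0 = −0.20, reject if z > 1.645.

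**3. Probability of claiming non-inferiority**, by exact enumeration of two independent binomials, 74 per arm:

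| Metal v plastic | Literal, +0.20 | Literal, −0.20 | Intended |
|---|---|---|---|
| 46% v 66% | 99.96% | 4.9% | 5.7% |
| 56% v 66% | 98.5% | 0.2% | 37.3% |
| 66% v 66% | 83.2% | 0.001% | 83.2% |
| 71% v 66% | 63.5% | about 0 | 95.1% |
| 76% v 66% | 39.2% | about 0 | 99.2% |
| 76.2% v 61.1% | 16.3% | about 0 | 99.9% |
| 86% v 66% | 5.2% | about 0 | >99.9% |

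Under the +0.20 reading the chance of a claim falls as metal improves. Under the −0.20 reading a claim is likely only if metal is far worse (82.1% at 26% v 66%). Neither sign repairs the inequality.

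**4. A single result.** Suppose plastic resolves in 49/74.

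- Metal 55/74 is 6/74 = 8.1 points better. With δ0 = +0.20 the restricted estimates are 0.7915 and 0.5915, SE = √[(0.7915×0.2085 + 0.5915×0.4085)/74] = 0.0741, and z = (0.0811 − 0.20)/0.0741 = −1.60. The literal rule withholds the claim.
- That rule makes the claim for every metal count from 0 to 54.
- Metal 44/74 is 5/74 = 6.8 points worse. With δ0 = −0.20, SE = √[(0.5213×0.4787 + 0.7213×0.2787)/74] = 0.0780, and z = (−0.0676 + 0.20)/0.0780 = 1.70. The intended rule makes the claim from 44 upward.

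**5. At 82 per arm** the pattern is the same. Literal (+0.20) v intended: 99.99% v 5.7% at 46% v 66%; 86.0% v 86.0% at equal rates; 16.7% v 99.9% at the meta-analysis rates.

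**The case against.** The strongest reply is that the intended test is clear. The bracketed labels are right, protocol 8.1 and 8.2 state the aim as showing metal non-inferior, and SAP 3.1.2 gives the method, sidedness, α, margin, decision rule and, in words, the null to be rejected. Only one coherent test fits these. Literal coding would call 0/74 metal against 49/74 plastic non-inferior, which someone would notice. Protocol 8.6.2 also asks for endpoint estimates by arm "as well as differences between treatment groups and their 95% confidence intervals", so a reversed claim would sit beside a contradictory estimate. At the design assumption the literal (+0.20) and intended rules have identical power. The −0.20 reading has no direct textual support, since the margin is given as 20% with no sign.

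Most of this stands, and it makes the harm conditional: a careful statistician would probably program the right test. It does not remove the error. All four formal statements contradict the surrounding text, and the null value and tail have to be deduced. The confidence interval has no stated bound against which non-inferiority would be judged, so it can expose a reversal but does not supply the rule. The −0.20 reading matters only because it shows that a lost minus sign cannot explain the text.

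**Conclusion.** The concern holds. As written, the primary hypotheses do not express the claim that the trial is meant to test, under either sign of Δ, and they contradict the labels and sample-size text around them. If they are coded literally with Δ = +0.20, the primary conclusion can reverse: a near-certain claim for a stent 20 points worse, and about a one-in-six chance of a claim at the rates the plan's own literature review reports. If the analyst follows the labels and sample-size text, the result is unaffected.

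The probabilities assume independent binomial outcomes, complete data at 74 or 82 per arm, the Farrington-Manning statistic and a 1.645 cut-off. The intended test's 5.7% at the margin is the usual small excess of that approximation over 5%. Because this is the primary decision rule, it must be corrected before the analysis. The difference between 74 and the reproduced 69 to 70 per arm is a separate matter and errs on the safe side.

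**What to change.** In the protocol synopsis, protocol 8.1, SAP section 1 and SAP 3.1.1, replace the two displayed lines with:

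- H0: π_test − π_control ≤ −0.20 (metal inferior)
- Ha: π_test − π_control > −0.20 (metal non-inferior)

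Replace the lead sentence in each place with: *Under the null hypothesis, resolution with metal stents is lower than with plastic stents by 20 percentage points or more.*

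In SAP 7.3, add that the Farrington-Manning test uses a null difference of −0.20 (metal minus plastic) and rejects in the upper tail at one-sided 0.05. The sample-size paragraphs already name the correct null and need no change on this point.

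The cost is wording in four hypothesis statements and one sentence of SAP 7.3. Sample size and data collection stay as they are. The SAP part can be handled under SAP 5.6, in a revised plan approved before the analyses are run. The two protocol statements may need an amendment with ethics approval under protocol section 12, if the sponsor judges that the correction affects the scientific integrity of the data.
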